11.7. Handling and Disposal

Investigational product reconciliation must be performed at the site by the investigator and the monitoring team using treatment log forms and documented on the site's investigational product inventory countersigned by the investigator and the monitoring team.

After reconciliation authorization by the sponsor, all used, partially used, and unused vials and all original packaging will be disposed of locally (as required) or by the sponsor. This process will be provided to the site by the sponsor's designee.

12. STUDY PROCEDURES AND ASSESSMENTS

Subjects will provide written informed consent before any study-related procedures are initiated, including the cessation of prohibited concomitant therapy.

For the timing of assessments and procedures throughout the study, refer to the Schedule of Assessments (see [Table 1](#)). Throughout the study, every reasonable effort should be made by study personnel to follow the timing of assessments and procedures in the schedule of events for each subject. Visits performed after the Visit 2 baseline visit should be scheduled relative to Visit 2 in order to maintain 56 days of open-label treatment and administration every 14 days (± 3 days). If a subject misses a study visit for any reason, the visit should be rescheduled as soon as possible. Each study visit window after Visit 2 is ± 3 days. Visit procedures should be performed in the order shown however adjustments may be made to the order to accommodate site-specific requirements.

12.1. Study Periods and Visits

12.1.1. Screening (Visit 1)

The subject must be screened within 14 weeks before enrollment in the study. The following procedures will be performed at screening:

1. Obtain written informed consent
2. Review inclusion/exclusion criteria
3. Conduct genotyping for DcR3 genes (CD only)
4. Collect demographic information
5. Record medical and medication history
6. Perform a complete physical examination, including measurements of weight
7. Collect vital signs, including systolic and diastolic blood pressures, pulse, respiration rate and temperature
8. Perform 12-lead ECG
9. Collect blood samples for clinical laboratory tests
10. Perform QuantiFERON-TB Gold (QFT) blood test, or PPD tuberculosis skin test. If the subject's PPD tine skin test is ≥ 5 mm, a confirmatory chest x-ray is required.
11. Collect blood sample for β -hCG test (for females of childbearing potential only)
12. Collect stool sample for *C. difficile* and fecal calprotectin analyses
13. Collect urine sample for urinalysis
14. Collect urine sample for drug testing as warranted
15. Administer the CDAI (CD only)
16. Administer the IBD-Q questionnaire
17. Conduct the endoscopy with biopsy

18. Assess and record any AEs and concomitant medications
19. Provide access to patient diary to record daily assessment of the following:
 - a) Abdominal pain, general well-being and number of stools including loose or watery stool (e.g., 6 or 7 on Bristol stool form scale) and daily abdominal pain severity (scale of 0 to 10) for CD patients.
 - b) Stool frequency and rectal bleeding for UC patients.
20. Calculate the Modified Mayo Score (excluding the PGA component) using the endoscopy score from the central reader and self-reported data on stool frequency and rectal bleeding from the period prior to the subject being screened.

NOTE: Stool samples may be obtained at any time during the visit. Subjects who fail to meet clinical laboratory entry requirements may be re-tested as part of the screening period. Extensions of the screening window to accommodate clinical laboratories re-testing timeframes (excluding endoscopy with biopsy) are permitted as agreed with medical monitor.

12.1.2. Eligibility Check/Wash-Out Period

Each subject will receive a telephone call to confirm continued subject eligibility. For subjects not requiring a wash-out period the subject may return for Visit 2 once the diary has been completed for a minimum of 7 days immediately prior to dosing. Visit 2 should be completed no sooner than Day 8 from the time diary completion was initiated. Any changes in concomitant medication use and any newly occurring AEs since the last evaluation will be recorded.

With the exception of subjects who most recently received the biologic certolizumab pegol (Cimzia), subjects requiring a wash-out will have a blood test administered 8 weeks after their last dose of biologic treatment to ensure that serum levels of any previous biologic treatments are below the level of detection. If it is confirmed that the levels of previous biologic treatment are undetectable and the subject has completed the diary for a minimum of 7 days immediately prior to dosing, the subject may return for Visit 2. Visit 2 should be completed no sooner than Day 8 from the time diary completion was initiated. If the test results indicate that the previous biologic treatment is detectable, the subject will be required to complete a full 12-week wash-out period. For subjects receiving the biologic certolizumab pegol (Cimzia) a 12-week wash-out is required. The diary should be completed up to the time of the visit. Any changes in concomitant medication use and any newly occurring AEs since the last evaluation will be recorded.

If the subject is not eligible, the subject should have any changes in concomitant medication use and any newly occurring AEs since the last evaluation recorded and should be removed from screening.

12.1.3. Open-Label Treatment Period

12.1.3.1. Baseline Visit (Visit 2, Day 0)

12.1.3.1.1. Before Dosing

Prior to administration of the first dose of investigational product on Day 0, the following procedures will be performed:

1. Review inclusion/exclusion criteria to confirm continued eligibility or screen failure status.

NOTE: If the subject continues to be eligible for the study, the subsequent procedures should be performed. If the subject is not eligible, the subject should have any changes in concomitant medication use and any newly occurring AEs since the last evaluation recorded and should be removed from screening.
2. Perform a complete physical examination, including measurements of height and weight
3. Collect vital signs, including systolic and diastolic blood pressures, pulse, respiration rate and temperature
4. Collect blood sample for clinical laboratory tests
5. Collect blood sample for plasma MDGN-002 concentration and PK analysis
6. Collect blood sample for plasma ADA analysis
7. Collect blood sample for exploratory analyses as defined in [Table 1](#)
8. Collect urine sample for urinalysis
9. Collect urine sample for urine β -hCG test (for females of childbearing potential only)
10. Administer the CDAI (CD only)
11. Administer the IBD-Q
12. Review diary completion
13. Assess and record concomitant medications and newly occurring AEs since the last evaluation

In addition, ongoing AEs from the previous visit will be assessed and any change in their status will be recorded.

12.1.3.1.2. Dosing and 60 Minutes Post-Dosing

After completing the assessments shown in [Section 12.1.3.1.1](#), subjects will receive MDGN-002 by SQ injection in the abdomen in a zone of 4 to 10 cm from the umbilicus with the injection site rotated with each subsequent dose. Vital sign assessments will be conducted within 60 minutes post-dosing.

Subjects will remain in the clinic for 60 minutes after the investigational product has been administered. During this time, the following details will be recorded:

1. Any AEs occurring after dosing
2. Any concomitant medications administered after dosing
3. Assess subject response and available results against individual stopping rules criteria defined in [Section 8.5.1](#).

After completion of the post-dosing assessments, the subject may leave the clinic.

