The total duration of participation is approximately 26 weeks. Subjects will be required to visit the study center up to 12 times inclusive of 1 additional follow-up safety visit. During the study, subjects will participate in safety and efficacy assessments as well as pharmacokinetic blood sampling; DcR3 genotyping (CD only); measurement of LIGHT (Lymphotoxin-like, exhibits Inducible expression, and competes with Herpes Virus Glycoprotein D for Herpesvirus Entry Mediator, a receptor expressed by T lymphocytes), selected cytokines; ribonucleic acid (RNA) sequencing; flow cytometry of peripheral blood leukocytes; and quality of life assessment. Subjects currently receiving treatment with biologic therapies will be required to participate in a wash-out period, during which biologic treatment will be discontinued.

Number of patients (planned):

Approximately 14 total subjects will be enrolled as follows:

- 4 subjects with CD in the 1 mg/kg cohort
- 4 subjects with CD in the 3 mg/kg cohort
- 6 subjects with UC in the 3 mg/kg cohort

Diagnosis and main criteria for inclusion:

Inclusion criteria - Crohn's Disease:

1. Subject is able to speak English fluently and has provided written informed consent for this study.
2. Subject is male or female, ≥ 18 to ≤ 75 years of age.
3. Subject has a documented diagnosis of CD via endoscopy/colonoscopy and histological confirmation. Prior documentation of histological confirmation is acceptable.
4. Subject has moderate to severe, active CD as evidenced by Simple Endoscopy Score for Crohn's Disease (SES-CD) score of ≥ 7 .
5. Subject has failed treatment with an approved therapeutic dose of an anti-TNF α monoclonal antibody treatment with either no initial response (primary non-responder) or an initial response to induction with subsequent lost response (secondary non-responder) as defined in the protocol.
6. Subject can be receiving concurrent treatment with an oral corticosteroid, and/or azathioprine or 6-mercaptopurine (6-MP) or methotrexate (MTX) as defined in the protocol.
- 7.
8. Subject agrees to be genotyped at the DcR3 locus.

Exclusion criteria - Crohn's Disease:

1. Subject has a diagnosis of ulcerative colitis (UC) or indeterminate colitis.
2. Subject is unable to tolerate or unwilling to undergo study procedures including endoscopy and biopsy during the study.
3. Subject with signs or symptoms of bowel obstruction with small bowel imaging supporting obstruction.

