^c After Day 0 (Visit 2), visits at which MDGN-002 is administered should occur every 14 ± 3 days. These visits should be scheduled relative to Day 0 (Visit 2), which is the baseline visit.

^d Medical history will include details regarding all UC/CD-related surgical procedures and hospitalizations.

^e A complete physical examination will be performed at Visits 1, 2, 6, and 10/ET. Brief physical examinations will be done at Visits 4 and 8. Height will be measured at V2 only.

^f Vitals will be taken pre-and post-dose on Visit 2, 4, 6 and 8. Post-dose vitals should be taken at least 60 minutes post-dose, immediately prior to discharge.

^g TB testing will include QuantiFERON-TB Gold (QFT) blood testing or PPD skin testing. If the subject's PPD tine skin test is ≥ 5 mm, a chest x-ray will also be employed for TB assessment.

^h Clinical laboratory assessments at Visits 1, 6, and 10/ET include: CBC with differential, hematology, serum albumin, CRP, liver panel, GGT. Anti-drug antibodies will be measured at Visits 2, 6 and 10. Clinical laboratory assessments at Visits 2, 4, and, 8 include hematology and serum albumin.

ⁱ Pre-dose PK blood samples will be obtained within 60 minutes prior to dose at Visits 2, 4, 6 and 8.

^j Exploratory analyses will examine LIGHT, cytokines, RNA sequencing, and flow cytometry.

^k Serum β -hCG will be conducted at Visit 1 and Urine β -hCG tests will be conducted on Visits 2, 6 and 10.

^l Screening for amphetamines, barbiturates, benzodiazepines, cocaine, opiates, phencyclidine, cannabinoids, propoxyphene, and methadone as warranted.

^m Stool samples will be obtained at Visits 1, 6 and 10/ET. C.difficile test will be performed only at Visit 1. Fecal calprotectin will be measured at all specified visits.

ⁿ Histological confirmation of disease is performed only at Visit 1. Documentation will be provided to site for confirmation or prior documentation of histological confirmation is acceptable. Exploratory biomarker histology will be completed for samples provided to study central laboratory provider.

^o Adverse event monitoring begins at the time informed consent is signed.

^p Subjects will be required to remain in the clinic for at least 60 minutes after MDGN-002 administration for adverse event monitoring.

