12.3.1.2. Vital Signs

Vital signs, including systolic and diastolic blood pressure, pulse, and respiration rate, will be collected as shown in the Schedule of Assessments (see [Table 1](#)). Vital signs must be within the ranges listed below during Screening (Visit 1) and prior to enrollment at Visit 2:

- Blood Pressure: 80/50 to 140/90 mm/Hg
- Respiratory Rate: 8-20 breaths per minute
- Pulse: 50-120 beats per minute
- Temperature: 97.8°F to 99.1°F (36.5°C to 37.3°C)/average 98.6°F (37°C)

Vital signs will be taken pre- and post-dose at Visits 2, 4, 6 and 8. Pre-dose vital signs should be taken within 60 minutes before dosing. Post-dose vital signs should be taken at least 60 minutes after dosing, prior to discharge. Additional blood pressure and pulse measurements may be performed, as determined by the investigator, in order to ensure appropriate monitoring of subject safety and accurate recording of vital sign measurements. Any changes from baseline deemed clinically significant by the investigator are to be recorded as AEs.

The same method of blood pressure measurement (auscultatory or oscillometric) should be used and documented throughout the study for all subjects. In addition, the conditions of vital signs measurements should be controlled and as consistent as possible in order to minimize variability of the readings. It is advised that measurements be collected at a comfortable room temperature with little to no background noise, using the same (appropriately sized) cuff placed at the same location on the same arm. The cuff should have a bladder length that is 80% and a width that is at least 40% of arm circumference (a length-to-width ratio of 2:1).

The subject should be asked to remove all clothing that covers the location of cuff placement. The subject should not have exercised or consumed caffeine, alcohol, or nicotine within 30 minutes of collection. The subject should be comfortably seated, with the legs uncrossed, with feet flat on the floor, and the back and arm supported, such that the middle of the cuff on the upper arm is at the level of the right atrium (the mid-point of the sternum). The subject should be instructed to relax as much as possible for at least 5 minutes prior to collection. The subject should remain quiet during this time and throughout the measurement.

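### The four dosing-visit sections set post-dose vital signs at up to 60 minutes; Table 1 and Section 12.3.1.2 set them at 60 minutes or later, before discharge

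*Protocol*

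**What the plan says.** The protocol gives the timing of post-dose vital signs in two ways.

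- **Visit sections.** Sections 12.1.3.1.2 (Visit 2), 12.1.5 (Visit 4), 12.1.5.2 (Visit 6) and 12.1.5.4 (Visit 8) all carry the same sentence: "Vital sign assessments will be conducted within 60 minutes post-dosing". Each keeps the subject in the clinic for 60 minutes and then closes with "After completion of the post-dosing assessments, the subject may leave the clinic".
- **Schedule and vital-signs section.** Table 1 footnote f (Section 8.1) reads "Post-dose vitals should be taken at least 60 minutes post-dose, immediately prior to discharge". Section 12.3.1.2 reads "Post-dose vital signs should be taken at least 60 minutes after dosing, prior to discharge". Both name Visits 2, 4, 6 and 8.

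Two other places bear on which instruction governs. Section 12 states: "For the timing of assessments and procedures throughout the study, refer to the Schedule of Assessments". Table 1 footnote p states: "Subjects will be required to remain in the clinic for at least 60 minutes after MDGN-002 administration for adverse event monitoring".

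On the analysis side, SAP 9.4 summarizes vital signs by disease, cohort, visit and a pre-/post-dose time point, and gives no window in minutes. SAP 5.8 bases most safety summaries on nominal assessment times.

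**The concern.** One instruction sets 60 minutes as the latest time for the reading and the other sets it as the earliest. They apply to the same procedure at the same visits.

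The footnote f reading is a check immediately before the subject leaves. The visit sections contain no such check. They ask for vital signs some time in the first hour and let the subject go once that hour's assessments are complete. A site that works from its visit section can comply with it in full by taking vital signs a few minutes after injection and not repeating them.

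Safety and tolerability are the primary objective. Section 8.3 asks for special attention to hypersensitivity reactions, including anaphylaxis. Under Section 12.3.1.2, vital-sign changes that the investigator judges clinically significant become adverse events. When the reading is taken therefore affects what it can detect. In the SAP 9.4 tables, readings from shortly after injection and readings from discharge could sit under one post-dose label, with planned groups of only 4, 4 and 6.

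**Working it through.** The plan gives no figure to reproduce. The check is a comparison of texts followed by a count.

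**1. Compare the windows.** Let t be the minutes from injection to the post-dose reading.

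| Source | Visits | Condition |
|---|---|---|
| 12.1.3.1.2 | 2 | t ≤ 60 |
| 12.1.5 | 4 | t ≤ 60 |
| 12.1.5.2 | 6 | t ≤ 60 |
| 12.1.5.4 | 8 | t ≤ 60 |
| Table 1 footnote f | 2, 4, 6, 8 | t ≥ 60, immediately before discharge |
| 12.3.1.2 | 2, 4, 6, 8 | t ≥ 60, before discharge |

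For a single reading, t ≤ 60 and t ≥ 60 hold together only at t = 60. A reading at 30 minutes meets the visit section and breaches footnote f. A reading at 65 minutes does the reverse.

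**2. Is a single reading the right assumption?** Section 12.3.1.2 schedules vital signs before and after dosing, with one timing rule for each. It does not describe an early set and a separate discharge set. The visit sections schedule one post-dose set. In the 60-minute stay they otherwise ask for adverse events and concomitant medications, and at Visits 2, 6 and 8 for the individual stopping criteria. One scheduled post-dose set is the natural reading.

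**3. Which text governs?** Section 12 points to Table 1 for timing. The dedicated vital-signs section agrees with Table 1. Footnote p's minimum stay of 60 minutes fits a reading at discharge. All three point the same way, so the four visit sections are in error. Section 12.3.1.2 also uses a limit of within 60 minutes for the pre-dose reading, so the visit-section wording may have been carried over from there; that is inference.

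**4. Does the SAP resolve it?** No. SAP 9.4 has one post-dose time point with no minute limits, and SAP 5.8 uses nominal times.

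**5. How much data is open to either instruction?** The inputs are the planned enrolment in the Synopsis ("Approximately 14 total subjects will be enrolled as follows": 4 CD at 1 mg/kg, 4 CD at 3 mg/kg, 6 UC at 3 mg/kg) and the four dosing visits.

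- Summary cells: 3 disease/cohort groups × 4 visits = 12.
- CD 1 mg/kg: 4 subjects × 4 doses = 16 readings.
- CD 3 mg/kg: 4 × 4 = 16 readings.
- UC 3 mg/kg: 6 × 4 = 24 readings.
- Total: 16 + 16 + 24 = 56 readings.

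The cell count leaves out the CD Total column shown in SAP Section 5, which repeats the same readings. The 56 assumes 14 subjects who each receive all four doses. Missed doses would lower it. Replacement of subjects who withdraw before a third dose (Section 8.7) could raise it.

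**The case against.** The strongest reply is that a site reading the whole protocol reaches one answer: Section 12 points to Table 1, and Section 12.3.1.2 agrees. The conflict would then be editorial. That argument settles which text is right, but it does not make the other text harmless. The visit sections are the step-by-step instructions for each dosing day, and all four carry the wrong limit.

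A second reply is that both instructions can be met by taking two sets, since Section 12.3.1.2 says "Additional blood pressure and pulse measurements may be performed, as determined by the investigator". This is correct, and it means the clash depends on one post-dose set being taken. But the extra measurements are optional, cover blood pressure and pulse only, and are left to the investigator. Nothing in the visit sections prompts a second set.

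Third, early departure is not allowed under either wording, and adverse events are observed for 60 minutes in any case. This stands. What may be missing is the discharge measurement, not the observation period.

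Fourth, the analytic consequence is small. The analysis is descriptive, no hypothesis is tested (SAP 5.6), no stopping criterion in Section 8.5 is a vital-sign threshold, baseline is unaffected because it precedes dosing (SAP 5.1), and individual values are listed. All of this stands and limits the weight of the point. So does the fact that the documents do not show whether any site took readings early.

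**Conclusion.** The contradiction is real and lies in current, operative protocol text. The visit sections are wrong as written; Table 1 footnote f and Section 12.3.1.2 state the timing to follow. Twelve post-dose cells and about 56 planned readings are open to either instruction, on the assumptions of one scheduled post-dose set per dosing visit and four doses in each of 14 subjects. Those counts show the reach of the conflict; they do not estimate any bias, and how many readings were taken early is unknown.

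This is a minor correction. It should still be made, because the discharge reading is a safety measure in a study whose primary objective is safety, and because the post-dose tables otherwise have no single defined time.

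**What to change.** In Sections 12.1.3.1.2, 12.1.5, 12.1.5.2 and 12.1.5.4, replace the post-dose vital-signs sentence with the timing already in footnote f and Section 12.3.1.2: no earlier than 60 minutes after dosing and immediately before discharge. The cost is one sentence in each of four places, with no new procedure beyond what Table 1 already requires.

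Secondarily, in SAP Listing 16.2.9.1 (Vital Sign Measurements), add a derived column with the actual minutes after dosing for each post-dose reading. This is possible only if vital-sign and dosing times were recorded. Section 12.3.2.1 says so for PK sample times; no equivalent statement was found for vital signs. If dosing has already finished, this column is the part that still helps, since it tells the reader what each post-dose value represents.

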12.1.4. Visit 3 (Day 7 [\pm 3 days])

Subjects will return to the clinic on Day 7 (\pm 3 days), at which time the following procedures will be performed:

1. Collect blood samples for plasma MDGN-002 concentration and PK analyses
2. Assess and record any AEs and concomitant medications
3. Review diary completion

Assess subject response and available results against individual stopping rules criteria defined in [Section 8.5.1](#). In addition, ongoing AEs from the previous visit will be assessed and any change in their status will be recorded.

12.1.5. Visit 4 (Day 14 [\pm 3 days])

Subjects will return to the clinic on Day 14 (\pm 3 days), at which time the following procedures will be performed prior to dosing:

1. Perform a brief physical examination, including measurement of weight
2. Collect vital signs, including systolic and diastolic blood pressures, pulse, respiration rate and temperature
3. Collect blood sample for clinical laboratory tests
4. Collect blood samples for plasma MDGN-002 concentration, PK and ADA analyses
5. Administer the CDAI (CD only)
6. Review diary completion
7. Assess and record concomitant medication use and any newly occurring AEs since the last evaluation

In addition, ongoing AEs from the previous visit will be assessed and any change in their status will be recorded.

After completing these assessments, subjects will receive MDGN-002 by SQ injection in the abdomen in a zone of 4 to 10 cm from the umbilicus with the injection site rotated with each subsequent dose. Vital sign assessments will be conducted within 60 minutes post-dosing.

Subjects will remain in the clinic for 60 minutes after the investigational product has been administered. During this time, the following details will be recorded:

1. Any AEs occurring after dosing
2. Any concomitant medications administered after dosing.

After completion of the post-dosing assessments, the subject may leave the clinic.

